### **(3) Research progress on the role of Sapylin in cancer**

Currently, many studies have proven that Sapylin, as an immune adjuvant, has demonstrated definite efficacy and good prospects in various cancers, such as lung cancer, breast cancer, gastric cancer, and bladder cancer. Xie Chuanhua, Zhang Lin, Li Xuezhen, and others observed the efficacy of nebulized Sapylin combined with chemotherapy in the treatment of advanced non-small cell lung cancer (NSCLC) and found that nebulized Sapylin inhalation can improve chemotherapy efficacy and the body's immune function without obvious side effects. Yano et al. found through basic in vitro experiments that the cytotoxic effect of OK-432 on lung cancer cell lines increased in a dose-dependent manner and induced alveolar macrophages to produce various cytokines, namely IL-1, Tumor Necrosis Factor- $\alpha$  (TNF- $\alpha$ ), and IL-6. Based on in vitro experiments, they subsequently treated 6 patients with bronchioloalveolar carcinoma with pulmonary metastasis via nebulized OK-432 inhalation and found that no adverse reactions were observed in any patients, and the production of TNF- $\alpha$  by alveolar macrophages or anti-tumor cytotoxic activity was enhanced; however, the clinical efficacy of nebulized Sapylin on bronchioloalveolar carcinoma still requires further study. Zhang et al. treated the lung cancer cell line A549 with different concentrations of Sapylin and detected the proliferation, apoptosis, and signaling pathway expression of A549 cells. They found that Sapylin promoted apoptosis in a dose- and time-dependent manner and inactivated the PI3K/AKT and WNT3a/ $\beta$ -catenin signaling

pathways, suggesting that Sapylin has the effect of inhibiting lung cancer cell proliferation and promoting apoptosis. In addition, Li Dong et al., through a retrospective analysis of 100 lung cancer patients with pleural effusion, found that intrapleural perfusion of Sapylin can reduce malignant pleural effusion, lower the levels of cellular inflammatory factors and tumor markers in serum and pleural effusion, and alleviate the toxicity of single-agent Cisplatin perfusion chemotherapy. Kong et al. included 120 patients undergoing modified radical mastectomy for breast cancer in a prospective continuous cohort study and proved that Sapylin can stimulate the body to secrete various cytokines and promote wound healing. Studies abroad have also shown that the in vivo and in vitro application of the streptococcal preparation OK-432 can induce the production of tumor growth inhibitory factors in human monocytes. Similar to the above results, Ono et al. found through in vitro cell experiments that the streptococcal preparation can inhibit nucleic acid synthesis in tumor cells, thereby exerting an anti-tumor effect. Therefore, studying the effect of Sapylin on patients with NPC and evaluating its safety has important clinical significance.

Previously, through extensive literature review, we found that while Sapylin administered via traditional methods can reduce malignant pleural effusion and improve immunity in cancer patients, patients experience reactions such as injection site pain and fever. In contrast, the nebulized inhalation method is not only safe and effective but also improves the patient's immunity, inhibits tumor cell proliferation, and enhances the efficacy of tumor chemotherapy drugs. Furthermore, we have currently collected 32 clinical cases (16 cases in the CCRT + Sapylin group, 16 cases in the CCRT + Dexamethasone group). The results revealed that nebulized Sapylin inhalation can improve the efficacy of CCRT and prolong patient survival, improve the incidence and severity of RIOM in NPC patients, and show no obvious toxic side effects. However, the application of nebulized Sapylin in cancer treatment is currently only seen in lung cancer studies both domestically and internationally. Whether its application in NPC patients can improve the efficacy of concurrent chemoradiotherapy and what its safety profile is like are rarely reported domestically or internationally and require further research and exploration. Therefore, we intend to explore the impact of Sapylin on the efficacy of concurrent chemoradiotherapy and the incidence and severity of RIOM in NPC patients via nebulized inhalation, aiming to find a highly efficient, low-toxicity method for NPC specialists and patients that can reduce the occurrence and severity of RIOM and improve the efficacy of CCRT.

## II. Research Content

### 1. Research Objectives and Significance

#### 1.1 Research Objectives

(1) Primary Objective: The primary objective evaluated will be the incidence and severity of RIOM.

(2) Secondary Objectives: Secondary objectives include the duration of RIOM, the completion rate of the planned treatment regimen, the incidence and severity of adverse events as graded by CTCAE V5.0, as well as changes in body mass index (BMI).

#### 1.2 Research Significance

This study intends to explore the impact of nebulized Sapylin inhalation on the therapeutic efficacy of CCRT in patients with NPC via nebulized inhalation, observe the effect of nebulized Sapylin inhalation on the incidence and severity of RIOM, and evaluate the safety of nebulized Sapylin inhalation. This study aims to find a highly efficient and low-toxicity method for NPC specialists and patients to reduce the occurrence and severity of RIOM and improve the efficacy of CCRT.

## **2. Research Goals and Content**

### **2.1 Research Goals**

The purpose of this study is to investigate the effects of atomized inhalation of Sapylin versus Dexamethasone on the incidence and severity of RIOM, and to further evaluate the safety and effectiveness of aerosol inhalation of Sapylin and Dexamethasone in NPC patients receiving CCRT. This study will provide NPC specialists and patients with an efficient and low-toxicity method to reduce the occurrence and severity of RIOM and improve the efficacy of CCRT.

### **2.2 Research Content**

Under the guidance of Randomized Controlled Trial (RCT) principles, patients will be divided into an experimental group and a control group. Patients will receive standardized treatment using the designed clinical treatment protocol, changes in patients' clinical observation indicators during treatment will be recorded, and follow-up records will be made according to the scheduled time to collect clinical data. Using statistical methods for comprehensive analysis, the results of this study will provide scientific research evidence for exploring methods to improve the occurrence and severity of RIOM and enhance the efficacy of CCRT.

## **3. Research Protocol**

### **3.1 Study Design Type**

Non-inferiority, parallel-design, randomized controlled clinical study.

### **3.2 Research Methods**

#### **(1) Incidence and Severity of RIOM**

Guided by the principles of RCT, this study provides scientific research evidence to explore methods for improving the occurrence and severity of RIOM and enhancing the efficacy of CCRT. Specialized clinicians will observe whether patients develop RIOM and assess its severity during daily rounds, recording these in the progress notes. Grading will be performed using the WHO oral toxicity scale. The incidence and severity of RIOM will be statistically analyzed after the completion of concurrent chemoradiotherapy.

#### **(2) Duration of Radiation-Induced Oral Mucositis (RIOM)**

The duration of Radiation-Induced Oral Mucositis (RIOM) will be calculated from the day of its initial diagnosis (any grade) until the day it resolves to Grade 0 or baseline level, with this duration being assessed and documented daily in the medical records by the attending clinician during ward rounds.

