### 3.6 Patient Follow-up

(1) Observation and follow-up personnel will conduct patient follow-up via outpatient visits, telephone tracking, home visits, etc., to observe and evaluate the patient's RIOM grading, adverse effects, and weight changes

(2) Follow-up time requirements: The follow-up duration is set at 3 months, with assessments once a month.

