## **4. Duration of Participation (Time per session and total time)**

This study is expected to last 5 years, including an 48-month enrollment period. Each patient will be followed up for 12 months after stopping treatment.

- (1) Planned date for enrollment of the first patient: July 30, 2022.
- (2) Planned date for enrollment of the last patient: July 1, 2026.
- (3) Planned date for the last patient's exit or trial conclusion: July 1, 2027.
- (4) Estimated report date: July 20, 2027.
- (5) Follow-up duration: 12 months; Primary endpoint: Incidence and severity of RIOM; Secondary endpoints: ①Duration of RIOM; ②Rate of completion of treatment measures; ③Adverse events classified according to CTCAE 5.0; ④Changes in BMI

Follow-up frequency: The follow-up period is 1 year; The first follow-up is 1 month after concurrent chemoradiotherapy; thereafter, follow-up visits are every 3 months. RIOM incidence rate, severe RIOM incidence rate, ORR, and PFS.

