## VIII. Preliminary Research Foundation and Working Conditions

The research team conducted a retrospective study on 32 NPC (NPC) patients from 2016 to 2019. The study observed the effect of nebulized Sapylin and Dexamethasone on the incidence rate of RIOM (radiation-induced oral mucositis) and the efficacy of CCRT (Concurrent

Chemoradiotherapy) during concurrent chemoradiotherapy. Results showed: The CCRT combined with nebulized Sapylin group had a lower incidence rate of RIOM and Grade III-IV RIOM compared to the CCRT combined with nebulized Dexamethasone group (43.75% vs 68.75%) and (12.5% vs ≥31.3%), respectively. Furthermore, the CCRT combined with nebulized Sapylin group was superior to the CCRT combined with nebulized Dexamethasone group in terms of objective response rate (ORR) (87.5% vs 62.5%), median overall survival (OS) (53.7M vs 46.4M), and median progression-free survival (PFS) (27M vs 23M). Moreover, comparison of the efficacy and survival analysis between the CCRT combined with nebulized Sapylin group and the CCRT combined with nebulized Dexamethasone group revealed that the nebulized Sapylin inhalation group showed a trend toward reducing the incidence rate of Grade III-IV RIOM and enhancing CCRT efficacy in NPC patients, with no obvious toxic side effects observed. Therefore, this project will conduct a non-inferiority, parallel-design, randomized controlled study of nebulized Sapylin versus nebulized Dexamethasone for the prevention and treatment of radiation-induced oral mucositis in NPC.

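### Duration of RIOM has a value only for patients who develop RIOM, and its daily ward-round measurement does not match the sparse, conflicting follow-up visits

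*Protocol*

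**What the plan says.** Section 1.1 makes this a secondary endpoint: "Secondary objectives include the duration of RIOM". Section 3.2 (2) defines it as "calculated from the day of its initial diagnosis (any grade) until the day it resolves to Grade 0 or baseline level". On how the days are to be captured, that section relies on inpatient observation alone, "with this duration being assessed and documented daily in the medical records by the attending clinician during ward rounds". It assigns no value to a patient without RIOM and gives no rule for RIOM still present at the last contact. The LOCF rule in section 7 is stated for primary variables only.

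Section 3.6 provides for grading after treatment. Staff will "conduct patient follow-up via outpatient visits, telephone tracking, home visits, etc". The stated purpose of these contacts is "to observe and evaluate the patient's RIOM grading, adverse effects, and weight changes". The schedule there is: "The follow-up duration is set at 3 months, with assessments once a month". Part III, section 4 sets a 12-month follow-up with a different schedule: "The first follow-up is 1 month after concurrent chemoradiotherapy; thereafter, follow-up visits are every 3 months". The table in section 4 (Research Design) also gives 1 year.

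Part VIII reports pilot RIOM incidence, Sapylin first, as "43.75% vs 68.75" per cent, with 16 patients per group.

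**The concern.** There are two problems.

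First, the start of the interval is a diagnosis day, so only patients who develop RIOM have a duration. Whether a patient develops RIOM is part of the primary outcome and is what treatment is meant to change. A between-arm comparison of durations so defined is conditioned on a post-randomisation event, and randomisation no longer protects it. If one treatment prevents some cases, the cases left in that arm may be a different mix from those in the other arm. The difference in duration then reflects that mix as well as any effect on how long mucositis lasts.

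Second, the end of the interval is a calendar day read from daily ward rounds. Mucositis may outlast treatment, and section 3.6 plans for that by grading it in follow-up. Those visits are at least a month apart, and the protocol gives two schedules for them. For episodes that end after ward rounds stop, the day of resolution is not recorded to the precision that the definition assumes.

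The stake is a secondary result that could understate, or under some conditions misstate, the effect on time spent with mucositis.

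**Working it through.** **Step 1. Reproduce the pilot incidence.** Input: RIOM row of Table 2, part VIII. Counts at Grades 0/I/II/III/IV are 9/1/4/2/0 (Sapylin) and 5/2/4/3/2 (dexamethasone).

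- Sapylin: (16 − 9)/16 = 7/16 = 43.75%.
- Dexamethasone: (16 − 5)/16 = 11/16 = 68.75%.

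Both match the stated figures.

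**Step 2. Patients with no duration at the planned size.** Input: 90 per arm (section 3.3). Formula: 90 × (1 − incidence).

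- Pilot rates: 90 × 9/16 = 50.6, about 51 (Sapylin); 90 × 5/16 = 28.1, about 28 (dexamethasone). That leaves about 39 and 62 with a value.
- 80% in both arms (the Background puts incidence above 80%): 90 × 0.20 = 18 per arm without a value, 72 with one.

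**Step 3. Can conditioning on cases matter?** The protocol gives no durations by grade, so those below are assumptions for illustration. Mean among cases = Σ(count × days)/number of cases. Mean over all = the same sum/16.

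Assume 14, 28, 42 and 49 days for Grades I to IV.

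- Pilot counts, Sapylin: 1×14 + 4×28 + 2×42 = 210. Among cases 210/7 = 30.0; over all 210/16 = 13.1.
- Pilot counts, dexamethasone: 2×14 + 4×28 + 3×42 + 2×49 = 364. Among cases 364/11 = 33.1; over all 364/16 = 22.8.
- Hypothetical Sapylin arm: take the dexamethasone counts and prevent only Grade I and half of Grade II, leaving 0/2/3/2. Sum 2×28 + 3×42 + 2×49 = 280. Among cases 280/7 = 40.0; over all 280/16 = 17.5.

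| Scenario (Sapylin vs dexamethasone) | Mean days among cases | Mean days over all patients |
|---|---|---|
| Pilot counts | 30.0 vs 33.1 | 13.1 vs 22.8 |
| Only mild cases prevented | 40.0 vs 33.1 | 17.5 vs 22.8 |
| 28 days for every case, 7 vs 11 cases | 28 vs 28 | 12.25 vs 19.25 |
| Exponential, shortest cases prevented | 43.6 vs 30.0 | 19.1 vs 20.6 |

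The last row assumes a control mean of 30 days among cases and prevention of the shortest 25/68.75 = 36.4% of cases. The cut is −30 × ln(1 − 0.364) = 13.6 days, and the mean of the remainder is 13.6 + 30 = 43.6. Over all patients: 0.4375 × 43.6 = 19.1 and 0.6875 × 30 = 20.6.

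The direction reverses in rows two and four. It does not reverse with the pilot counts, and with equal durations the comparison among cases shows no difference.

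**Step 4. Precision of the resolution date.**

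| Source | RIOM assessment | Resolution known to within |
|---|---|---|
| Section 3.2 (2) | Daily, ward rounds | 1 day, while rounds continue |
| Section 3.6 | Monthly for 3 months | About 1 month |
| Part III, section 4 | 1 month, then every 3 months to 12 months | About 1 month, then about 3 months |

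A midpoint date could be wrong by up to half the interval: about 15 days for a 30-day gap and about 45 days for a 90-day gap.

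**The case against.** Section 3.2 (2) describes how an episode is measured. It names no analysis set, summary or test for duration. A 0-day rule, the handling of unresolved episodes and the method of comparison are often left to a statistical analysis plan, which is not at hand. Duration among cases is also a legitimate descriptive quantity, and this endpoint plays no part in the sample size or the primary comparison. Most of this stands, and it limits the point to a secondary endpoint. It does not remove it: the start and stop days are fixed in the protocol, and on that definition a RIOM-free patient has no value. A 0-day rule elsewhere would amend the definition rather than fill it in.

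A reader might infer three stronger things that the documents do not support.

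- That the protocol excludes RIOM-free patients from the comparison. It is silent. The omission follows from the definition but is not stated.
- That resolution after discharge cannot be observed. Section 3.6 schedules RIOM grading by outpatient visit, telephone or home visit, so the date is interval-censored. Nor does the protocol give a discharge date.
- That Sapylin will look worse on duration. Reversal needs durations that rise with grade, or prevention confined to short episodes. In the pilot, Sapylin also had fewer severe cases (Grade III 2 vs 3, Grade IV 0 vs 2).

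**Conclusion.** The point holds for a secondary endpoint. As defined, duration exists only for patients who develop RIOM, so a between-arm comparison on it is not a randomised comparison and could mislead. About 51 vs 28 of 90 per arm would have no value if pilot incidence recurs, and about 18 per arm if incidence is 80% in both. The first figure rests on 16 retrospective patients per group graded by CTCAE version 5, whereas section 3.2 (1) grades by the WHO scale. A reversal of direction is possible under some assumed durations but is not shown by the pilot data. Separately, daily ward-round measurement does not fit either follow-up schedule, and the two schedules contradict each other. Resolution after ward rounds stop is known only to within about one to three months. The primary non-inferiority conclusion is not affected.

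**What to change.** - For the between-arm comparison, define the endpoint as the number of days with RIOM Grade 1 or higher from Day 1 of CCRT to the 1-month visit, in all FAS patients, with 0 days for patients who never develop RIOM. Both schedules share this visit if the monthly assessments in section 3.6 run from the end of treatment, which should be stated.
- Treat resolution between the last ward-round grade and that visit as interval-censored by a pre-stated rule: for example the midpoint, with the earliest and latest possible dates as sensitivity analyses. RIOM still present at the visit counts to the end of the window.
- Report duration among RIOM cases descriptively, beside the main comparison.
- Reconcile section 3.2 (2), section 3.6 and part III, section 4 on when RIOM is graded after treatment.

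The cost is a change of endpoint wording and a small change in analysis. Ward-round grades are already planned, but they do not cover the gap before the 1-month visit, so the interval rule is needed. The new endpoint combines occurrence and length, which is why the descriptive figure must sit beside it. The window also ends a month after CCRT, so its length varies with treatment time, planned at 6 to 7 weeks. The text should say so.

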#### **(3) Completion Rate of Treatment Modalities**

The completion rate of treatment modalities will be determined by recording the actual

administered dose and number of cycles of concurrent chemoradiation therapy (CCRT) versus the planned total regimen; this rate is calculated as two ratios: the actual administered dose divided by the planned total dose, expressed as a percentage, and the actual completed cycles divided by the planned total cycles, also expressed as a percentage.

#### (4) Adverse Events (AEs)

All observed adverse events (AEs) will be recorded and graded daily by the clinician based on patient complaints, physical examination, and laboratory test results, according to the Common Terminology Criteria for Adverse Events (CTCAE) version 5.0 published by the National Cancer Institute (NCI).

#### (5) Change in Body Mass Index (BMI)

Patient height and weight will be measured by the nursing staff at a fixed time using the same calibrated instrument at two time points—before the initiation of CCRT (baseline) and upon completion of treatment—with the resulting BMI ( $kg/m^2$ ) difference (*post-Treatment BMI-Baseline BMI*) constituting the change in BMI.

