### **3.3 Inclusion and Exclusion Criteria and Sample Size Estimation**

(1) Patient Selection: Meeting the diagnostic criteria for NPC; patients who have not yet received concurrent chemoradiotherapy; meeting the case inclusion and exclusion criteria; patients voluntarily joining this clinical trial and signing the informed consent form.

(2) Sample Size Estimation: The Delphi method is used to determine the non-inferiority margin of the observation endpoint. After consulting senior oncology practitioners, we defined an 8% reduction in the incidence of RIOM as a clinically acceptable non-margin of error. Under the conditions of test level  $\alpha=0.05$  and test efficacy  $1-\beta=0.9$ , the proportion of cases in the two groups is 1:1. Using the module of non-destructiveness Tests for Two Proportions in PASS 15.0 statistical analysis software, we determined that a sample size of 81 was required per group. Considering a 10% loss to follow-up rate, we estimated that 90 cases would be required in each group, for a total of 180 cases.

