### **3.5 Clinical Treatment Protocol**

#### (1) Experimental Group

Concurrent Radiotherapy Dose: Nasopharyngeal primary tumor site (PTVnx): 69.96Gy/2.12Gy/33F; High-risk planning target volume (PTV1): 60.06Gy/1.82Gy/33F; Low-risk

planning target volume (PTV2): 54.12Gy/1.64Gy/33F; Cervical lymph nodes (PTVnd): 66~69.96Gy/2~2.12Gy/33F; 5 times per week, for a total of 6-7 weeks.

Concurrent Chemotherapy: Cisplatin (80-100 mg/m^2, Q3W, 3 times during CCRT); Sapylin: 1 KE/time, nebulized, QD, starting from Day 1 of CCRT until the end of radiotherapy.

(2) Control Group:

Concurrent Radiotherapy Dose: Nasopharyngeal primary tumor site (PTVnx): 69.96Gy/2.12Gy/33F; High-risk planning target volume (PTV1): 60.06Gy/1.82Gy/33F; Low-risk planning target volume (PTV2): 54.12Gy/1.64Gy/33F; Cervical lymph nodes (PTVnd): 66~69.96Gy/2~2.12Gy/33F; 5 times per week, for a total of 6-7 weeks.

Concurrent Chemotherapy: Cisplatin (80-100mg/m^2, Q3W, 3 times during CCRT); Dexamethasone: 10mg/time, nebulized, QD, starting from Day 1 of treatment until the end of radiotherapy.

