### (2) Statistical Analysis

① General Principles: One-sided tests will be used for superiority tests, while two-sided tests will be used for other statistical tests. Quantitative indicators will be described using the number of cases, mean, standard deviation, median, minimum, and maximum. Categorical indicators will be described using the number of cases and percentages. All statistical analyses will be conducted using SPSS 26.0 statistical software.

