### **III. Study Participant Recruitment**

#### **1. Inclusion Criteria**

- (1) stage III-IVa NPC (AJCC 8th edition) diagnosed via pathology in a tertiary hospital;
- (2) no previous radiotherapy, chemotherapy, surgery, immunization, or targeted therapy;
- (3) Karnofsky Performance Status score  $\geq 80$ ;
- (4) intact and normal oral mucosa before treatment;
- (5) age 18–75 years;
- (6) voluntary participation and provision of informed consent in person;
- (7) routine blood examination: white blood cell count  $\geq 4.0 \times 10^9/L$ , hemoglobin  $\geq 100g/L$ , neutrophil count  $\geq 1.5 \times 10^9/L$ , and platelet count  $\geq 100 \times 10^9/L$ ;
- (8) biochemical examination: total bilirubin  $\leq 1.5 \times$  the upper limit of the normal range (ULN), alanine aminotransferase and aspartate aminotransferase  $\leq 2 \times$  ULN, and estimated glomerular filtration rate  $\geq 60$  mL/min.

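### Height is re-measured for the second BMI, which adds a small, avoidable measurement error to the BMI-change secondary endpoint

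*Protocol*

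**What the plan says.** The Protocol, section II, 3.2(5), sets out how BMI change is obtained: "Patient height and weight will be measured by the nursing staff at a fixed time using the same calibrated instrument at two time points". The two occasions are "before the initiation of CCRT (baseline) and upon completion of treatment". The difference between the two resulting BMI values, post-treatment minus baseline, is described as "constituting the change in BMI". The text does not say that one height serves for both values, so its natural reading is that each BMI is built from the height and weight taken at that visit.

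Three other places matter. Radiotherapy is given "5 times per week, for a total of 6-7 weeks" (section II, 3.5). Eligible patients are adults, "age 18–75 years" (section III, 1). Section II, 6 lists change in BMI as the fourth of four secondary indicators.

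The statistical section (II, 7(2)) names no test or model for BMI change. Its only general rule on testing is: "One-sided tests will be used for superiority tests, while two-sided tests will be used for other statistical tests".

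**The concern.** BMI is weight divided by height squared. In adults followed for 6-7 weeks, weight can move but height cannot to any meaningful degree. A second height reading therefore tells us nothing about the patient that the first did not. Any gap between the two readings comes from posture, positioning or reading error. Because height enters as a square, a relative error in height becomes about twice that relative error in BMI, and the difference between visits carries the errors of both readings.

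At stake is some precision on a secondary endpoint: a wider interval for the arm difference in BMI change than the weight data require. What is measured and how the outcome variable is built are fixed in the Protocol itself, so the point concerns a stated rule and not a detail left open for the statistical analysis plan.

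**Working it through.** The Protocol states no SD, effect size, power or height error for BMI, so there is no figure of its own to reproduce.

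**Inputs from the Protocol**
- Height and weight both taken at two visits; outcome is the BMI difference (II, 3.2(5)).
- 81 evaluable patients per arm: "we determined that a sample size of 81 was required per group" (II, 3.3). This number was set for mucositis incidence and is borrowed here only to give a scale.
- Equal allocation: "the proportion of cases in the two groups is 1:1" (II, 3.3).

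**Assumed inputs (not in the Protocol)**
- BMI 23 kg/m² and height 165 cm, used for both visits.
- SD of a single height reading 0.5 or 1.0 cm, errors independent between visits.
- SD of BMI change without height error 1.0, 1.5 or 2.0 kg/m².
- Two-sided 0.05 and 90% power for the detectable difference.

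**Step 1: error SD added to BMI change.** With BMI = weight/height², a small height error e shifts BMI by about 2 × BMI × e/height. Two independent readings give

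error SD = √2 × 2 × BMI × SD(height)/height

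- 0.5 cm: 1.414 × 2 × 23 × 0.5/165 = 0.197 kg/m²
- 1.0 cm: 1.414 × 2 × 23 × 1.0/165 = 0.394 kg/m²

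**Step 2: added variance, (error SD / SD of change)².**

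| SD of BMI change | 0.5 cm | 1.0 cm |
|---|---|---|
| 1.0 | 3.9% | 15.5% |
| 1.5 | 1.7% | 6.9% |
| 2.0 | 1.0% | 3.9% |

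**Step 3: detectable difference at 81 per arm.** Formula: total SD × √(2/81) × (1.960 + 1.282), where total SD = √(SD of change² + error SD²).

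| SD of BMI change | One height | Two heights, 0.5 cm | Two heights, 1.0 cm |
|---|---|---|---|
| 1.0 | 0.509 | 0.519 | 0.548 |
| 1.5 | 0.764 | 0.771 | 0.790 |
| 2.0 | 1.019 | 1.024 | 1.038 |

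At SD 1.0 the inflation factors are √1.039 = 1.019 and √1.155 = 1.075. These ratios do not depend on the significance level or power chosen.

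**Step 4: the same loss in patients, SD 1.0.** Of 162 evaluable patients, the effective number is 162/1.039 = 155.9 (about 6 lost) at 0.5 cm, or 162/1.155 = 140.3 (about 22 lost) at 1.0 cm.

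**The case against.** The strongest reply is that the effect is close to negligible and that no figure in the Protocol shows it matters. This largely stands. At 0.5 cm error and SD 1.0 the detectable difference moves by 0.519 − 0.509 = 0.010 kg/m². The 15.5% figure needs both a 1 cm reading error and the smallest SD considered. The Protocol asks for the same calibrated instrument at a fixed time, and any error shared by both readings largely cancels in the difference. The independence assumption is then an upper figure to the extent that errors are shared. Posture and reading errors are not removed by using one instrument, however, so some noise remains. Endpoint rank also counts: no power, margin or decision rule is attached to BMI change.

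Two stronger readings are tempting, and the Protocol supports neither.

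- A reader might infer that baseline BMI is ignored, or that an unadjusted comparison has been fixed where ANCOVA is needed. The definition subtracts baseline BMI, so baseline is in it. It fixes the outcome variable, not the model; section II, 7(2) neither names a model for BMI change nor excludes a baseline covariate. With baseline BMI as covariate, analysing the change or the post-treatment value gives the same treatment estimate. An unadjusted change is in any case unbiased under randomisation. The choice of model is commonly left to a statistical analysis plan, which is not at hand, so its absence is no defect here.
- A reader might infer that the second height biases the arm comparison. If the reading error is alike in both arms, it adds scatter only.

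**Conclusion.** The point holds as a minor measurement remark. The Protocol prescribes a second height that carries no information and, on its natural reading, lets that height's error into a secondary endpoint. The consequence is lost precision, without bias between arms if the error is alike in both.

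The plausible cost is about 1-4% of variance at 0.5 cm reading error and 4-16% at 1.0 cm. This range rests wholly on assumed values for BMI, height, independence of errors and SD of BMI change (1.0-2.0 kg/m²), because the Protocol supplies none of them. Severity is low. The primary endpoint, the sample size and the main conclusion are unaffected. The case for acting is that the correction is free.

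**What to change.** In section II, 3.2(5), state that height is measured once, at baseline, that only weight is re-measured at completion of treatment, and that both BMI values are calculated with the baseline height. The endpoint can stay as post-treatment minus baseline BMI, and the analysis model can stay with the statistical analysis plan.

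The cost is one clause of text and one measurement fewer per patient. If second heights have already been recorded for some patients, no data need be discarded: the second BMI is recalculated from the recorded weight and the baseline height, by the same rule in both arms.
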